7.2.3 Study Visit Flowsheet

Screening Visit – Visit 1	6-Week Follow-Up – Phone Call
Enrollment, Randomization, Pre-injection VAS, Injection, Post-injection VAS x 2, objective hand exam (SOC)	VAS, trigger question

7.3 Duration of Participation

Subjects will only be seen in the clinic site once (time of enrollment in study) and will be contacted via telephone six weeks post-injection.

7.4 Test Article(s) (Study Drug(s) and/or Study Device(s))

7.4.1 Description

The study drugs consist of the following:

- CS – corticosteroid alone -1 cc dexamethasone (4mg/ml) only
- CSL – corticosteroid/lidocaine combination - 1 cc dexamethasone (4mg/ml) and 1 cc 1% lidocaine
- CSS – corticosteroid/saline combination - 1 cc dexamethasone (4mg/ml) and 1 cc 0.9% injectable saline)
-

All of these drugs are currently FDA approved and considered standard of care.

7.4.2 Treatment Regimen

The study investigator will perform a single injection using a 25 gauge 1.5" needle. The needle will be inserted at 90 degrees to the skin, 1 cm proximal to the metacarpophalangeal joint flexion crease.

7.4.3 Method for Assigning Subject to Treatment Groups

Patients will be randomized to receive CS, CSL, or CSS during their clinic visit.

7.4.4 Subject Compliance Monitoring

After obtaining informed consent, patients will be randomized to one of three recruitment groups. They will then be asked to complete a Patient Survey pre-injection and again 1 minute and 10 minutes after injection. They will be contacted via phone at six weeks post-injection and asked to verbally complete the Patient Survey.

7.4.5 Blinding of the Test Article

The three drug combinations will be compounded in the Bone & Joint Institute as part of routine standard of care.

7.4.6 Receiving, Storage, Dispensing and Return

7.4.6.1 Receipt and Storage of Test Article

The compounds will be stored at room temperature in the Bone & Joint Institute. These injections are routine standard of care and all policies regarding receipt, storage, dispensing and disposing will be strictly followed.

7.4.6.2 Preparation and Dispensing

Subject randomization will be performed prior to dispensing of any study drugs. After randomization, subjects will be dispensed study drugs as follows:

- CS – corticosteroid alone - 1 cc dexamethasone (4mg/ml) only
- CSL – corticosteroid/lidocaine combination - 1 cc dexamethasone (4mg/ml) and 1 cc 1% lidocaine
- CSS – corticosteroid/saline combination - 1 cc dexamethasone (4mg/ml) and 1 cc 0.9% injectable saline)

7.4.6.3 Return or Destruction of the Test Article

The study drug will be disposed of in clinic following standard procedure for disposal of needles.

7.4.6.4 Prior and Concomitant Therapy

See exclusion criteria

8.0 Data and Specimen Banking For Future Undetermined Research

8.1 Data and/or specimens being stored – N/A

8.2 Location of storage – N/A

8.3 Duration of storage – N/A

8.4 Access to data and/or specimens – N/A

8.5 Procedures to release data or specimens – N/A

8.6 Process for returning results– N/A**9.0 Statistical Plan****9.1 Sample size determination**

Sample size was determined based on a review of prior studies that used the VAS as the main outcome tool. A total sample size of 221 was determined based on the number needed to detect a difference of 5 mm assuming a standard deviation of 10 mm in the VAS and when also considering a 15 % drop out rate. 221 total patients initially enrolled in the study would account for 64 patients per treatment arm (Corticosteroid only v corticosteroid/lidocaine v corticosteroid/saline). Public Health Sciences will be ensuring accuracy of statistical analyses. Stratification based on perioperative variables of interest will not be necessary in our study. Instead, we will be analyzing these variables via subgroup multivariate analyses at the conclusion of the study.

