7.2 Study Procedures**7.2.1 Visit 1 – Screening/Baseline Visit**

Patients will be given information about the study and asked to participate. If eligible, based on inclusion and exclusion criteria, informed consent will be obtained at the time of the screening visit and the patient will be enrolled in the study.

After obtaining informed consent, the patient will be randomized to one of three treatment groups. The study investigator (who is unblinded) will randomly draw a sealed envelope

containing one of the three treatment groups. The sealed envelopes will be stored in a secure area within the clinic practice site.

- CS – corticosteroid alone -1 cc dexamethasone (4mg/ml) only
- CSL – corticosteroid/lidocaine combination - 1 cc dexamethasone (4mg/ml) and 1 cc 1% lidocaine
- CSS – corticosteroid/saline combination - 1 cc dexamethasone (4mg/ml) and 1 cc 0.9% injectable saline)

The patient will then be asked to complete a Patient Survey pre-injection (VAS Pain Scale and Trigger question). The study investigator will perform a single injection using a 25 gauge 1.5" needle. The needle will be inserted at 90 degrees to the skin, 1 cm proximal to the metacarpophalangeal joint flexion crease. The injections will be prepared in the Bone & Joint Institute as part of standard of care.

The patient will then complete the Patient Survey at 1 minute and 10 minutes following injection (VAS Pain Scale and Trigger question).

Objective hand exam will be performed including range of motion at MP, PIP and DIP joints, presence of clicking or locking, triggering score, pain with range of motion and grip strength as part of the patient's standard of care.

7.2.2 6-Week Follow-Up Phone Call

The patient will be contacted via phone and will be asked to verbally complete the Patient Survey (patient will be asked to report the VAS Pain score over the phone in .5 increments – i.e. 3.5, 4.0, 5.0, 5.5, etc.) and the coordinator will record the score. The patient will also answer question about how often he/she triggers (see phone script).

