9.2 Statistical methods

The daily average pain score (VAS) will be compared between groups using either t-test or Wilcoxon test for each of the 6 days after the operation. Chi-square tests will be used to compare treatment groups for categorical variables (satisfaction, presence of clicking/locking, adverse events). Level of significance will be set at $p < 0.05$.

Secondary statistical analysis will include multivariate analyses to determine which variables such as anatomic location and comorbidities will impact the VAS score or modify the efficacy of injection. These can be accomplished by adding these variables and their interaction with treatment groups in the regression model. As these are secondary analysis, any interesting findings will be subject to validation in future studies.

Any deviations from the previously described statistical plan will be described and justified in a protocol amendment.

All analyses comparing the treatment groups will be conducted on an intention-to-treat basis. Two-tailed tests will be used at all times.

There will be an interim analysis when 50 % of patients (n=111) are enrolled and have completed final visit testing.

10.0 Confidentiality, Privacy and Data Management**10.1 Confidentiality****10.1.1 Identifiers associated with data and/or specimens**

See the Research Data Plan Review Form

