16.0 Number of Subjects

Approximately 222 people (74 per treatment arm) will be enrolled in this research study at the Hershey Medical Center.

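### Minor: 221 enrolled with 15% dropout leaves about 63 patients per arm, not the 64 that section 9.1 states; 64 per arm allows for a loss of only about 13%

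*Combined protocol and SAP*

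**What the plan says.** Section 9.1 bases the total of 221 on a "difference of 5 mm assuming a standard deviation of 10 mm in the VAS and when also considering a 15 % drop out rate". It then states that "221 total patients initially enrolled in the study would account for 64 patients per treatment arm". It gives no power, names no time point for the 5 mm and the SD of 10 mm, and does not say what the 15% is a percentage of.

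Section 16.0 gives a slightly different total: "Approximately 222 people (74 per treatment arm) will be enrolled in this research study".

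The schedule bears on where dropout can act. In section 7.2.1, "The patient will then complete the Patient Survey at 1 minute and 10 minutes following injection", within the only clinic visit. The one later VAS score is the 6-week call in section 7.2.2: "The patient will be contacted via phone and will be asked to verbally complete the Patient Survey". Section 3.3.2 keeps data collected before withdrawal. It also says that further enrolment may be needed, but sets no target.

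**The concern.** Section 9.1 is the plan's only justification of the sample size. Three of its figures (221 enrolled, 15% dropout, 64 per arm) are presented as consistent, and a reader who applies a 15% loss to 221 does not arrive at 64. At stake is whether the number of patients per arm that the plan says it will have is the number its own enrolment and dropout figures deliver. A shortfall would reduce the precision of any comparison that depends on patients staying in the study.

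**Working it through.** **Inputs.** From 9.1: 221 enrolled, 15% dropout, 64 per arm, difference 5 mm, SD 10 mm. From 16.0: approximately 222 enrolled, 74 per arm. From 9.2: significance level 0.05, two-tailed. Assumed, because the plan states no power: 80%.

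**1. Reproduce the plan's 64.** Two-sample t-test, standardised difference 5/10 = 0.5, two-sided 0.05, 80% power (noncentral t): n = 63.77, rounded up to 64 per arm. Three arms: 3 x 64 = 192.

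**2. Reproduce the plan's 221.**
- Allowance added to the completers: 192 x 1.15 = 220.8, rounded up to 221. This matches.
- Allowance taken from those enrolled: 192 / 0.85 = 225.9, rounded up to 226. This does not match.

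The addition is 221 - 192 = 29 patients, and 29/192 = 15.1% of the completers.

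**3. Is 64 a number before or after dropout?** 221/3 = 73.7, and 16.0 gives 74 per arm enrolled. So 64 can only be the number after dropout.

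**4. Apply the stated dropout to those enrolled.**

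| Enrolled | Left after 15% loss | Per arm | Short of 64 by | Loss that leaves 192 |
|---|---|---|---|---|
| 221 | 221 x 0.85 = 187.85 | 62.6 | 1.4 | 1 - 192/221 = 13.1% |
| 222 | 222 x 0.85 = 188.7 | 62.9 | 1.1 | 1 - 192/222 = 13.5% |

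Steps 3 and 4 use only figures in the plan and do not depend on the assumed power.

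**5. Size of the effect, for illustration.** One unadjusted pairwise t-test, two-sided 0.05, 5 mm difference, SD 10 mm:

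| Per arm | Power | Difference detectable with 80% power |
|---|---|---|
| 64 | 80.1% | 4.99 mm |
| 62.9 (from 222) | 79.5% | 5.03 mm |
| 62.6 (from 221) | 79.3% | 5.05 mm |

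These figures show only how large the slip is. They do not describe a planned analysis: 9.1 names no time point, and 9.2 speaks of VAS scores "compared between groups using either t-test or Wilcoxon test for each of the 6 days after the operation", not of the 6-week call.

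**The case against.** **The 15% may be meant as a share of the completers.** On that reading 221, 64 and 15% agree, because 192 x 1.15 = 220.8, and 9.1 does not define the denominator. This explains how 221 probably arose, and it stands to that extent. But 9.1 calls the figure a dropout rate and speaks of patients initially enrolled. A dropout rate is ordinarily a share of those enrolled, and on that meaning 64 does not follow. If the other base was intended, 9.1 still has to say so.

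**The gap is immaterial.** Largely true. The enrolment that would keep 64 per arm after a 15% loss is 226, only 5 more than 221 (2.3%), and section 16.0 already treats its total as approximate. That settles the severity; it does not make the statement correct. Section 3.3.2 softens the consequence by allowing more enrolment, but with no target it does not turn 221 into 64 per arm.

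**The immediate pain scores are hardly affected.** Also true. The 1- and 10-minute scores are taken at the enrolment visit and earlier data are kept, so dropout should act mainly on the 6-week call.

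**Stronger readings.** A reader might infer that the trial is underpowered or has to enrol 226. The documents do not support this: the plan commits to no power, and the difference is under one percentage point in the illustration. A reader might also infer that the 6-week comparison specifically falls short of its planned power. The plan does not say that the 5 mm and SD 10 mm apply at 6 weeks, and 9.2 describes no 6-week VAS test.

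**Conclusion.** Minor, wrong as written. On the ordinary meaning of a dropout rate, 221 enrolled with 15% dropout gives 62.6 patients per arm (62.9 from 222), not 64, and 64 per arm corresponds to a loss of 13.1% (13.5% from 222). The likely cause is that 15% was added to the 192 completers without saying so; this is inferred from the exact match to 221.

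The shortfall is 1.1 to 1.4 patients per arm. The power comparison (about 79.3% to 79.5%, against 80.1%) rests on the 5 mm and SD 10 mm of 9.1 and on a single unadjusted pairwise t-test. The 80% reference is inferred from the 64 and is not stated in the plan. Nothing here calls the design, the enrolment or the analyses into question.

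**What to change.** Restate 9.1 along these lines: *64 per arm are required for a 5 mm difference with SD 10 mm; enrolling 222 (74 per arm) allows for about 13.5% dropout, and a 15% dropout would leave about 63 per arm.* This keeps the 64 that the 5 mm and SD 10 mm support and makes the dropout statement true.

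Use the same total in 9.1 and 16.0. The interim statement in 9.2, "There will be an interim analysis when 50 % of patients (n=111) are enrolled", needs no change: 222/2 = 111, and 221/2 = 110.5 rounds to the same number.

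Do not tie the 63 or 64 per arm to 6 weeks, or give a power figure for the 1- and 10-minute scores, unless the sponsor confirms the time point to which the 5 mm and SD 10 mm apply. A power figure is optional; if one is added, its assumptions should be stated with it.

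The cost is protocol wording only. One sentence becomes slightly less favourable, with no extra patients and no change to procedures or analyses.

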9.2 Statistical methods

The daily average pain score (VAS) will be compared between groups using either t-test or Wilcoxon test for each of the 6 days after the operation. Chi-square tests will be used to compare treatment groups for categorical variables (satisfaction, presence of clicking/locking, adverse events). Level of significance will be set at $p < 0.05$.

Secondary statistical analysis will include multivariate analyses to determine which variables such as anatomic location and comorbidities will impact the VAS score or modify the efficacy of injection. These can be accomplished by adding these variables and their interaction with treatment groups in the regression model. As these are secondary analysis, any interesting findings will be subject to validation in future studies.

Any deviations from the previously described statistical plan will be described and justified in a protocol amendment.

All analyses comparing the treatment groups will be conducted on an intention-to-treat basis. Two-tailed tests will be used at all times.

There will be an interim analysis when 50 % of patients (n=111) are enrolled and have completed final visit testing.

10.0 Confidentiality, Privacy and Data Management**10.1 Confidentiality****10.1.1 Identifiers associated with data and/or specimens**

See the Research Data Plan Review Form

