1.2 Primary Study Endpoints

- Compare pain and efficacy associated with the three treatment groups.
 - VAS and mean daily pain values

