2.2 Previous Data

Previous studies have evaluated the efficacy of steroid injections as compared to placebo injections in the treatment of trigger finger but no previous studies have compared steroid/lidocaine injections to injections without lidocaine. The aim of this study is to compare post-injection pain and efficacy of trigger finger injection using a combination of lidocaine/corticosteroid versus corticosteroid injection alone or corticosteroid/saline (equal volume). Our hypothesis is that lidocaine causes unnecessary pain upon injection and does not improve the efficacy of the steroid in providing sustained anti-inflammatory benefit. We also seek to determine if volume of injection plays a role in immediate post-injection pain (corticosteroid/saline group).

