11.3 Method of collection of safety information

Data will be collected beginning after informed consent at time of enrollment through six weeks postoperatively. Data will be collected at the initial clinic visit and again via telephone six weeks post-injection. Adverse events will be collected as they occur.

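### The only direct between-arm VAS test in section 9.2 needs six daily scores that the trial never collects, and the readings it does collect have no stated test or primary time point

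*Combined protocol and SAP*

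**What the plan says.** **Planned analysis.** Section 9.2 states: "The daily average pain score (VAS) will be compared between groups using either t-test or Wilcoxon test for each of the 6 days". The sentence goes on to count those days from an operation. Section 1.2 gives the primary endpoint as "VAS and mean daily pain values", covering both pain and efficacy, with no time point. The rest of 9.2 offers chi-square tests for categorical outcomes and a secondary regression asking which covariates affect VAS or modify efficacy. That regression names no VAS reading. Section 9.1 sizes the trial on a 5 mm VAS difference with SD 10 mm, again without saying which reading.

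**Planned data collection.**
- 7.2.1: a survey with VAS before injection, and then "The patient will then complete the Patient Survey at 1 minute and 10 minutes following injection (VAS Pain Scale and Trigger question".
- 7.2.3, under the 6-week call: "VAS, trigger question".
- 7.3: "Subjects will only be seen in the clinic site once (time of enrollment in study) and will be contacted via telephone six weeks post-injection".
- 7.4.4: "They will be contacted via phone at six weeks post-injection and asked to verbally complete the Patient Survey".
- 11.3: "Data will be collected at the initial clinic visit and again via telephone six weeks post-injection".

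**Aims.** Section 2.2 ties the pain question, including the role of volume, to the period right after the injection. Its efficacy hypothesis is that lidocaine "does not improve the efficacy of the steroid in providing sustained anti-inflammatory benefit".

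**The concern.** The analysis section and the schedule describe different data. If 9.2 is followed literally, the primary VAS comparison returns no result and someone has to choose a substitute. Three choices are open: the 1-minute or the 10-minute reading for pain, the t-test or the Wilcoxon test, and which pairs of the three arms to compare, since both tests take two groups.

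Section 9.2 asks for deviations to be justified in an amendment but sets no deadline. An interim analysis is planned at n=111, and 17.5 has the team reviewing data at regular meetings. Nothing suggests that a selective choice is intended. But the plan does not fix the choice in advance, so a reader of the results could not tell a prespecified primary result from one selected afterwards.

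**Working it through.** **1. Readings required against readings scheduled**

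| Time | Needed by 9.2 | Scheduled (7.2, 7.2.3, 7.3, 7.4.4, 11.3) |
|---|---|---|
| Pre-injection | no | yes |
| 1 minute | no | yes |
| 10 minutes | no | yes |
| Days 1 to 6, daily average | yes, 6 scores | none |
| 6 weeks (phone) | no | yes |

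Four readings are scheduled and 0 of the 6 needed daily scores is among them. Reading the operation as the injection does not help, because there is no contact between the clinic visit and the 6-week call.

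**2. The plan's own sample size**

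Inputs from 9.1 and 9.2: difference 5 mm, SD 10 mm, two-sided 0.05, dropout 15%. Power is not stated; 80% is assumed.

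- Normal approximation: n = 2(1.960 + 0.842)² × (10/5)² = 62.8, so 63 per arm. The exact two-sample t-test gives 63.77, so 64, which matches the plan.
- Total: 3 × 64 = 192, and 192 × 1.15 = 220.8, so 221, which also matches. (Dividing by 0.85 would give 226.)

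The trial is therefore sized for one two-arm comparison at one reading, and the plan does not say which reading or which pair.

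**3. Which collected readings fit the aims**

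Pain right after injection can be read at 1 or 10 minutes, so that choice is open. Sustained benefit can be read on VAS only at 6 weeks.

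**4. Cost of choosing the pain reading after seeing results**

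Simulation with no true difference: 100,000 trials, 3 arms × 64, two readings per patient. The correlation between readings is not in the documents and is assumed to lie between 0.3 and 0.9. A false positive is any p < 0.05.

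| Correlation | 0.3 | 0.5 | 0.7 | 0.8 | 0.9 |
|---|---|---|---|---|---|
| Overall F-test, either reading | 0.096 | 0.092 | 0.084 | 0.079 | 0.074 |
| Three unadjusted t-test pairs, either reading | 0.224 | 0.213 | 0.196 | 0.184 | 0.170 |

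With one fixed reading the rates are 0.050-0.051 for the F-test and 0.121-0.125 for the three pairs. Leaving the reading open therefore adds about 2 to 5 points (overall test) or 5 to 10 points (three pairs).

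**5. Power under the possible replacement rules**

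5 mm, SD 10 mm, two-sided 0.05, with no gain assumed from baseline adjustment. For a single pair at 64 per arm, the noncentrality is 0.5 × √(64/2) = 2.83, giving power 0.802. The other rules are for the pair that differs by 5 mm. Ranges cover third-arm means equal to one of that pair (0, 0, 0.5 SD) or midway (0, 0.25, 0.5 SD).

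| Rule | 64 per arm | 74 per arm |
|---|---|---|
| First contrast in a fixed order | 80% | 86% |
| Pair tested after an overall 3-arm gate | 70-76% | 77-83% |
| Holm over three pairs | 66-69% | 74-76% |

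**6. What a non-significant 6-week contrast would show**

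The 95% CI half-width at 64 per arm is 1.98 × 10 × √(2/64) = 3.5 mm. At assumed SDs of 15 and 20 mm it is 5.2 and 7.0 mm. With SD 10 mm, a true 2.5 mm lidocaine benefit would be non-significant in 71% of trials.

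**The case against.** The strongest points on the other side are these.

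- **Wording slip.** The 6 days may be a slip for 6 weeks. That would leave the daily average without meaning, would not explain the daily values in 1.2, and would still leave the 1- and 10-minute readings untested.
- **Unseen forms.** The survey form and phone script are not in the text, so a diary could exist. But the procedures, flowsheet, duration, compliance and safety sections give the contact and collection occasions, and none falls on days 1 to 6.
- **Secondary regression.** It could carry a treatment term, but it is a covariate and effect-modifier analysis, labelled secondary, with no reading named.
- **Data access.** Section 11.5 has the team reviewing all data at study completion, the data collector is blinded (7.1), and 17.5 does not say that its review is by arm. This weakens the case for ongoing exposure to results. It does not remove it: an interim analysis is planned, the injecting physician is unblinded, and review at completion is itself too late to choose the analysis.
- **Status of efficacy.** Section 1.3 lists effectiveness as secondary, and the trigger question or clicking/locking could serve as efficacy measures. Section 1.2, however, places efficacy with pain under VAS as primary, so the 6-week VAS is a fair reading. The inconsistency should be settled in the same amendment.
- **Scale of the figures.** The false-positive rates are conditional illustrations that rest on an assumed correlation. This stands; the firm figure is 0 of 6.

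**Conclusion.** The concern holds with high confidence, and the text has to be corrected. The primary VAS comparison is wrong as written, not merely thin on detail: none of its 6 inputs is collected, and the 3 post-injection readings that exist have no stated direct between-arm test. That conclusion comes from comparing sections and needs no assumption.

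The effect on error rates does need assumptions: 64 per arm, a between-reading correlation of 0.3 to 0.9, and a choice between 1 and 10 minutes made on the results. The overall three-arm test used for the lower range is not named in the plan. The excess from three unadjusted pairs is a separate matter that would exist even if daily scores were collected.

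**What to change.** Amend before any outcome data are examined, including at the interim analysis. If any data by arm have already been seen, the amendment should say so.

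**Needed to repair the defect**
1. Replace the first sentence of 9.2 with an analysis of the VAS readings actually collected, and drop the daily means from 1.2.
2. Name one of the 1-minute and 10-minute readings as the primary pain outcome and the other as supportive. Name the 6-week VAS as the efficacy outcome.
3. Name one test. ANCOVA adjusted for the pre-injection VAS suits these data.
4. Name the contrasts implied by 2.2: CSL versus CSS (lidocaine at equal volume), CSS versus CS (volume) and CSL versus CS.

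**Advisable in the same amendment**

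5. State one multiplicity rule for the pain contrasts: a fixed order starting with CSL versus CSS, an overall 3-arm gate, or Holm.
6. Report the 6-week lidocaine contrast as an estimate with a 95% confidence interval whatever the pain result, since non-significance would not show an absence of benefit. If a no-benefit claim is wanted, state its margin.
7. Confirm where satisfaction, extra analgesic use and time to stopping medication are recorded. The procedures text shows no step for them, though forms outside the text may. This is a separate, minor point.

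**Cost.** Protocol wording only, with no new visits, readings or patients. The power price depends on item 5 and is tabulated in the working. A fixed order keeps full power for its first contrast but tests later ones only if the earlier ones are significant. Because the pain readings are taken at the enrolment visit, the 74-per-arm column (the enrolment target in 16.0) applies if nearly all patients supply them.

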7.0 Study Design and Procedures

7.1 Study Design

This will be a prospective, randomized, double-blind study in which patient and data collector is blinded to the treatment protocol. The physician who is preparing and performing the injection will remain unblinded.

Recruitment → Randomization → Treatment (Corticosteroid v corticosteroid/lidocaine v corticosteroid/saline)

Corticosteroid (CS) → post-injection assessment immediately following injection → post-injection assessment at 6 weeks (via phone)

Corticosteroid/lidocaine (CSL) combination → post-injection assessment immediately following injection → post-injection assessment at 6 weeks (via phone)

Corticosteroid/saline (CSS) combination → post-injection assessment immediately following injection → post-injection assessment at 6 weeks (via phone)

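### The main VAS comparison leaves out the pre-injection VAS; adjusting for it would cost almost nothing and gain precision by an uncertain amount

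*Combined protocol and SAP*

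**What the plan says.** Section 9.2 gives the main pain analysis in one sentence: the "pain score (VAS) will be compared between groups using either t-test or Wilcoxon test for each of the 6 days after the operation". It mentions no baseline term, change score or adjustment.

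The pre-injection score is a scheduled assessment for every patient. Section 7.2.1 states: "The patient will then be asked to complete a Patient Survey pre-injection (VAS Pain Scale and Trigger question". The flowsheet in 7.2.3 lists "Enrollment, Randomization, Pre-injection VAS, Injection, Post-injection VAS x 2", and section 7.4.4 repeats the sequence: "They will then be asked to complete a Patient Survey pre-injection and again 1 minute and 10 minutes after injection". A last VAS is taken by telephone at 6 weeks.

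The only regression in section 9.2 is labelled secondary. It asks which "variables such as anatomic location and comorbidities will impact the VAS score" or modify efficacy. Pre-injection VAS is not named there. Section 9.1 rules out stratification, so the design does nothing to balance starting pain.

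Two further statements bear on the remedy. Allocation comes before the pre-injection survey (section 7.2.1: "The study investigator (who is unblinded) will randomly draw a sealed envelope"), while section 7.1 says that the "patient and data collector is blinded to the treatment protocol". Section 9.2 also plans an early look at the data: "There will be an interim analysis when 50 % of patients (n=111) are enrolled".

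**The concern.** If pain before the injection predicts pain afterwards, part of the spread in the outcome can be explained by a score already in hand. An unadjusted test leaves that part in the error term, so each interval for a difference between arms is wider than it need be. Also, when the arms happen to differ in starting pain, the unadjusted estimate is shifted in that particular trial. The type I error allows for this on average, but the reported difference is not corrected for it.

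The trial has little to spare: its stated 64 per arm corresponds to about 80% power.

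A linked problem comes first. Section 9.2 tests scores on six successive days, whereas VAS is scheduled only before the injection, at 1 and 10 minutes, and at 6 weeks. An adjusted analysis cannot be specified until its outcome time is fixed.

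**Working it through.** **Inputs from the documents.** Difference 5 mm, SD 10 mm, 64 per arm, three arms, 15% dropout, 221 in total (section 9.1); about 222 enrolled, 74 per arm (section 16.0); two-sided tests at 0.05 (section 9.2).

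**Assumed.** Power of 80%, which is not stated; a baseline SD of 10 mm; the 10 mm SD taken as that of a post-injection score; and r over a range from 0.1 to 0.7, since no value is given.

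**The plan's own figure.** A two-sample t-test for 5/10 = 0.5 SD with 80% power needs 63.77, so 64, per arm. Then 3 × 64 = 192, and 192 × 1.15 = 220.8, so 221. The stated size is reproduced, and it makes no allowance for a baseline covariate.

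**Effect of adjustment at 64 per arm.**

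- Residual SD = 10 × √(1 − r²). For r = 0.3 this is 10 × √0.91 = 9.54 mm.
- Power comes from the noncentral t distribution with that SD.
- 95% CI half-width = t(0.975; 126) × SD × √(2/64). For r = 0 this is 1.979 × 10 × 0.1768 = 3.50 mm.
- Equivalent n is the smallest unadjusted size per arm with at least the same power.
- SE of the baseline difference between two arms = 10 × √(2/64) = 1.77 mm. The part that carries into the unadjusted result is r × 1.77.

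| r | Residual SD (mm) | Power | CI half-width (mm) | Equivalent n per arm | Carried imbalance, 1 SE (mm) |
|---|---|---|---|---|---|
| 0 (unadjusted) | 10.00 | 80.1% | 3.50 | 64 | 0 |
| 0.1 | 9.95 | 80.5% | 3.48 | 65 | 0.18 |
| 0.2 | 9.80 | 81.7% | 3.43 | 67 | 0.35 |
| 0.3 | 9.54 | 83.7% | 3.34 | 71 | 0.53 |
| 0.5 | 8.66 | 90.0% | 3.03 | 86 | 0.88 |
| 0.7 | 7.14 | 97.6% | 2.50 | 125 | 1.24 |

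**Cost of adjustment.** Losing one degree of freedom changes power by about 0.0001. Estimating the slope inflates the variance by about 1/124 = 0.8% in a two-arm model and 1/187 = 0.5% in a three-arm model. In a two-arm model this takes about 0.3 points off the power (at r = 0.1, 80.2% instead of 80.5%). In a three-arm model the larger pooled error degrees of freedom make this up, and the tabulated figures hold to within 0.01 points.

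**Sensitivity to n.** The 1- and 10-minute scores are taken at the enrolment visit, where little dropout is likely. If all 74 per arm contribute, power is 85.6% unadjusted, 86.9% at r = 0.2 and 88.6% at r = 0.3. The gain at r = 0.3 is then 3.1 points instead of 3.6.

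**A change score is not an equal substitute.** With equal SDs its SD is 10 × √(2(1 − r)). At r = 0.3 this is 11.8 mm, which is worse than no use of baseline at all; it equals 10 mm only at r = 0.5.

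**The case against.** The strongest reply is that nothing here is wrong: the unadjusted test is valid under randomisation, and the benefit of adjusting may be slight. That is fair, and it limits the weight of the point. The 1-minute score largely reflects pain from the injection itself. At 10 minutes, the quick relief that section 2.1 attributes to lidocaine could weaken the link with starting pain in that arm. At 6 weeks, the relief in 47% to 87% of patients cited in section 2.1 could pile scores near zero. The rows for r = 0.5 and 0.7 therefore have no support in the documents. At r of 0.2 or less the power gain is under 2 points and the half-width shrinks by at most 0.07 mm.

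The table also takes the t-test as its reference. Section 9.2 allows a Wilcoxon test instead, and no gain over that has been computed.

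The covariate is recorded after an unblinded investigator has drawn the envelope. If a patient learned the allocation at that moment, the score could be affected, and adjusting would bring that into the main result. The unadjusted test does not have this dependence. The plan describes the patient as blinded, so the covariate is usable, but the reliance is real.

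Finally, the secondary regression does not exclude pre-injection VAS. But a list of examples in a secondary model does not pre-specify the main comparison. The mismatch of time points is the larger defect in the same sentence; once it is repaired, the comparison would still be unadjusted.

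**Conclusion.** The concern holds as an optional improvement in efficiency, not as an error. The main comparison gives no role to a score that every patient is scheduled to provide. At 64 per arm, 5 mm and SD 10 mm, using it would add 0.4 to 3.6 points of power for r between 0.1 and 0.3, and 9.8 points at r = 0.5. At r = 0 it gains nothing and costs at most about 0.3 points. The result rests on an unknown r, on 10 mm being the SD of the analysed score, on roughly normal-theory behaviour of VAS, and on patient blinding at the pre-injection survey.

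**What to change.** 1. Reconcile the time points analysed in section 9.2 with those collected in section 7.2. This is needed in any case.
2. Before any interim look, specify the main VAS comparison as an analysis of covariance on treatment arm, with pre-injection VAS as covariate and robust standard errors. Fix the model in advance, fit it to all three arms together, and report adjusted pairwise differences with 95% confidence intervals.
3. Name one time point and one pairwise contrast as primary. Three collected times and three contrasts give nine comparisons; label the other eight secondary. This is a separate decision, but the model statement is incomplete without it.
4. Keep one named unadjusted test as a sensitivity analysis, in place of the open choice between two.
5. State that the pre-injection VAS follows the envelope draw and that its use as a covariate relies on patient blinding. For patients still to be enrolled, recording it before the draw would remove that reliance.

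The adjustment itself adds a few sentences to an amendment of section 9.2 that is needed anyway, and uses one degree of freedom. It requires no new patients or measurements; only the optional reordering in step 5 touches clinic procedure. Choosing the primary time point and contrast takes more thought than drafting.
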